8.2 Mortality

- The number of all the patients receiving surgery as the denominator and the number of the patients in any of the following situations as the numerator are used to calculate proportions. This proportion indicated the operative mortality ratio.

- Situations: patients whose death was identified according to documented intraoperative observation items, including patients who die within 30 days after the surgery (including 30 days) regardless of the causality between the death and the surgery, and patients who die more than 30 days after the surgery (whose death is proved to have a direct causal relationship with the first operation).

8.3 Determination of surgical outcomes

8.3.1 Operative time: from skin incision to the skin being sutured

8.3.2 Postoperative recovery indexes

8.3.2.1 Time to ambulation, flatus, recovery of liquid diet and semi-liquid diet.

- During the day of surgery to the first discharge, the initial time to ambulation, flatus, liquid diet and semi-liquid diet during the postoperative hospitalization is recorded by

hour.

- Flatus on the operation day should be excluded.
- If flatus or resumption of liquid and semi-liquid diet does not occur before hospital discharge, the discharge time should be recorded as the corresponding time.
- The initial time to ambulation, flatus, liquid diet and semi-liquid diet should be recorded according to patients' reports.

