Outcome Measures	
Primary Outcome Measures :
 
 ● Overall postoperative morbidity rates 
Secondary Outcome Measures :
 
 ● Intraoperative morbidity rate ● Operative time ● Estimated blood loss ● Number of harvested and metastatic lymph nodes ● the lengths of incision, proximal and distal margins ● Time to first flatus ● Time to first liquid diet ● Postoperative hospital stay ● Total cost
Statistical considerations	
All data analyses will be performed using SPSS statistical software, version 23.0 (SPSS Inc), and the R software environment (R Foundation for Statistical Computing).
 
All data analyses will be conducted on a per-protocol (PP) basis. This study does not fill in missing values. Normally distributed continuous variables will be presented as mean and standard deviation and compared using the t-test if normally distributed, or as median and interquartile range and compared using the Wilcoxon rank-sum test if non-normally distributed; while categorical data will be presented as number and percentages and compared using the Pearson χ^2 test or the Fisher exact test, as appropriate. Sensitivity analysis is used for extreme outlier data. The confidence interval of the parameters is estimated with a 95% confidence interval. The central effect analysis and subgroup analysis are conducted according to the specific situation. All the statistical tests were tested by two sides. A p-value <0.05 is considered statistically significant.

1. Research background

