5.2 Secondary Outcome Measures

- Intraoperative morbidity rate
- Operative time
- Estimated blood loss
- Number of harvested and metastatic lymph nodes
- the lengths of incision, proximal and distal margins
- Time to first flatus
- Time to first liquid diet
- Postoperative hospital stay
- Total cost

6. Diagnostic criteria for this study

- (1) The AJCC-8th TNM tumor staging system will be used for this study.
- (2) Diagnostic criteria and classification of gastric cancer: According to the histopathological international diagnostic criteria, classification will be divided into

papillary adenocarcinoma (pap), tubular adenocarcinoma (tub), mucinous adenocarcinoma (muc), signet ring cell carcinoma (sig), and poorly differentiated adenocarcinoma (por).

(3) Definition of advanced stage: tumor infiltration of the stomach wall reaches or exceeds the inherent muscular layer (T2); T2, T3, and T4a patients will be included as study subjects, whereas T4b patients will not.

(4) Definition of esophagogastric junction carcinoma: According to the AJCC-8th tumor staging system, esophagogastric junction carcinoma is defined as a tumor whose tumor center is located within 5cm above and below the esophagogastric junction. According to Siewert classification, the tumor was divided into Siewert type I : the tumor center was located 1 ~ 5 cm above the esophagogastric boundary; Siewert type II : The center of the tumor was 1 cm to 2 cm above the esophagogastric boundary. Siewert type III : The tumor center is located 2 to 5 cm below the esophagogastric boundary. Only Siewert type III esophagogastric junction carcinoma were involved in this study.

7 Qualifications of the participated Surgeons

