9.3.3.4 Discharge standard

Patients needed to meet the following criteria for discharge: 1) satisfactory intake of a soft diet. 2) move around of their bed. and 3) absence of complications by routine clinical examinations. This information will be recorded in the CRF.

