10.1 Statistical analysis plan

- Statistical software: we will use SPSS statistical software, version 23.0 (SPSS Inc), and the R software environment (R Foundation for Statistical Computing) to perform statistical analyses.
- Basic principle: The method of differential testing was adopted. The safety population of the study consists of the patients who receive safety evaluation data after the intervention. Descriptive statistics and two-sided tests were conducted for the safety indicators and the incidence of adverse reactions. A p-value <0.05 is considered statistically significant. The confidence interval of the parameters is estimated with a 95% confidence interval.
- Shedding analysis: Total shedding rate of two groups and loss rate due to adverse events will be compared using pearson χ^2 test

- All data analyses will be conducted on a per-protocol (PP) basis.
- Method of outlier determination: the observation value is greater than P75 or less than P25, and the exceed value more than 3 times of the quartile spacing ($=p75-p25$), which will be sentenced to outlier data. During the analysis, the sensitivity analysis is used for outlier data, namely analyzing outcomes including or excluding outlier's data. and if the results are not contradictory, the data is retained; if the contradiction, it depends on the specific circumstances.
- Descriptive statistics: The measurement data gives the mean, the standard deviation and the confidence interval, and the minimum value, the maximum value, the P25, the median and the P75 are given when necessary; matched data also gives the mean and standard deviation of the gap-value, and the median and average rank of the Non-parametric method. The nominal-scale data gives the frequency distribution and the corresponding percentages. The level data gives the frequency distribution and the corresponding percentages, as well as the median and the average rank. Qualitative data give positive rate, positive number, and denominator numbers. The survival data gives the number of events, the number of deletions, the median survival time, and the survival rate.
- Subgroup analysis : Sub-group analysis is to find the factors that may affect prognostic according to the specific circumstances of the data.
- Missing values handling: This study does not fill in missing values

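### Discharge time is entered as the time to flatus or diet when neither has occurred by discharge, so a lower bound is analysed as an observed recovery time.

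*Protocol*

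**What the plan says.** Section 8.3.2.1 sets the observation window: "During the day of surgery to the first discharge, the initial time to ambulation, flatus, liquid diet and semi-liquid diet" are recorded in hours. It then deals with patients in whom the event is not seen: "If flatus or resumption of liquid and semi-liquid diet does not occur before hospital discharge", "the discharge time should be recorded as the corresponding time". It asks for no event indicator and does not mention censoring. The substitution covers flatus and the two diet items, not ambulation.

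Two of these items are secondary outcomes in section 5.2: "Time to first flatus" and "Time to first liquid diet".

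The statistical considerations in the Summary compare continuous variables by t-test if normally distributed; otherwise they are "compared using the Wilcoxon rank-sum test if non-normally distributed". Section 10.1 has measurement data described by mean, standard deviation and confidence interval, with the median added when necessary. It also puts all analyses on a per-protocol basis and adds: "This study does not fill in missing values".

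The discharge standard in section 9.3.3.4 asks for "satisfactory intake of a soft diet", mobility and absence of complications. Flatus is not among its criteria.

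**The concern.** A patient who goes home without flatus has a time to flatus longer than the stay. The rule enters the stay itself, which is the smallest value the unobserved time could take. Neither planned test can tell that number from a real recovery time.

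The error has a direction. Among patients who have not recovered, the earlier the discharge, the shorter and better the recorded time. An arm that discharges unrecovered patients sooner, or has more of them, is flattered. The study is open and non-randomized, so nothing in the design balances such discharges between arms. At stake is the comparison of two secondary recovery outcomes. The primary outcome, postoperative morbidity, is untouched.

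**Working it through.** The protocol gives no figure for these outcomes, so there is nothing to reproduce. The check has two parts: whom the rule reaches, and what it does to each summary.

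**Whom it reaches**

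- *Diet.* Section 9.3.3.4 requires soft-diet intake before discharge. A patient discharged under that standard should already have taken liquids, so this part of the rule is almost empty.
- *Flatus.* Not a discharge criterion, so a patient can meet the standard with no flatus reported. This is the part with real scope.
- *Early exits.* Section 4.3 withdraws patients who quit voluntarily (item 21) and some with sudden severe perioperative complications (item 20). With the per-protocol rule in 10.1, these would ordinarily not be in the comparison.

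The number left is small, and the protocol gives no count.

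**Assumptions for size** (only the 68 is from the protocol, section 3.3): n = 68 per arm; times log-normal with median 72 h and log-SD 0.3; k patients in one arm without flatus at discharge.

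**Effect on the mean.** With discharge at D and true recovery at T, the arm mean is understated by k(T − D)/n. The mean among recovered patients is 72 × exp(0.3²/2) = 75.3 h. Take D = 216 h. The substituted mean is [(68 − k) × 75.3 + k × 216]/68.

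| k | Mean with substitution | True mean, T = 240 h | True mean, T = 336 h | Understatement |
|---|---|---|---|---|
| 1 | 77.4 h | 77.7 h | 79.1 h | 0.35 to 1.8 h |
| 3 | 81.5 h | 82.6 h | 86.8 h | 1.1 to 5.3 h |
| 7 | 89.8 h | 92.3 h | 102.1 h | 2.5 to 12.4 h |

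**Effect on the median.** None in these settings. Simulated medians are 72.5, 73.3 and 75.3 h for k = 1, 3 and 7, whether the discharge time or the true time is used, because both lie above the middle of the distribution.

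**Effect on the Wilcoxon test.** Compare entering D with giving the patient the worst rank. Against 68 patients in the other arm, one patient changes the Mann–Whitney count by 68 × S(D), where S(D) is the share of recovery times longer than D. The null standard error (SE) is √(68 × 68 × 137/12) = 68 × 3.379. The shift per patient is therefore S(D)/3.379 SE.

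| Discharge of unrecovered patient | S(D) | Shift per patient |
|---|---|---|
| Uniform over 48 to 120 h | 0.376 (average) | 0.11 SE |
| 120 h | 0.0443 | 0.013 SE |
| 168 h | 0.00237 | 0.0007 SE |
| 216 h | 0.000125 | 0.00004 SE |

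For exits over 48 to 120 h, all in one arm, 1, 2, 3 or 5 patients shift the statistic by 0.11, 0.22, 0.33 or 0.56 SE in that arm's favour. For five patients at 216 h the shift is about 0.0002 SE: a late discharge time already ranks near the worst.

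**The case against.** The strongest reply is that the rule hardly ever applies and hardly matters when it does. Ordinary discharges need a soft diet and no complications, early leavers fall to the withdrawal criteria, and the rank test is indifferent to a late discharge time. All of this stands, and it limits the point to a minor one. It does not make the rule right: section 10.1 makes the mean the default summary, the t-test is used whenever the data are judged normal, and for both the entered value is too low.

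It can also be said that the detailed analysis plan, not shown, may hold a sensitivity analysis. That is possible, but the recording rule is fixed here. If the CRF keeps only the substituted time, these patients may not be identifiable later.

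Three stronger readings are tempting and are not supported:

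- *That an early death or transfer is scored as a recovery.* The rule speaks only of hospital discharge and names neither; mortality is defined separately in section 8.2.
- *That the rule flatly contradicts the statement on missing values.* The two sit awkwardly together, but 8.3.2.1 can be read as an endpoint definition for a known state, with the no-imputation rule applying to absent data. The protocol should say so.
- *That the rank comparison is materially biased.* The 0.56 SE needs five of 68 patients leaving unrecovered at about days 2 to 5, all in one arm and all kept in the per-protocol set. Nothing in the protocol suggests this.

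**Conclusion.** The point holds as a minor one: a stated rule treats a lower bound on an unobserved time as an observed recovery time in two secondary outcomes. It mainly concerns flatus and few patients. Means are understated, by 0.35 to 12.4 h in the cases shown; the upper end needs seven of 68 patients unrecovered at 216 h and recovering only at 336 h. The median is unchanged in those cases. The Wilcoxon comparison is affected only if unrecovered patients leave early. All sizes rest on the assumed distribution, discharge times and counts, since the protocol supplies none of them. Correcting it is desirable because it is cheap; no main conclusion of the study depends on it.

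**What to change.** In section 8.3.2.1, replace the substitution with wording such as: *If flatus, liquid diet or semi-liquid diet has not occurred by discharge, record the item as not reached by discharge and keep the discharge time separately. In the comparison between arms, these patients take the worst rank in a Wilcoxon rank-sum test. Report medians, and the number not reached in each arm.*

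In section 10.1, state that this is an endpoint definition and not imputation. Reconcile the diet part of 8.3.2.1 with the discharge standard in 9.3.3.4, since under that standard it should almost never be needed.

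A log-rank comparison that censors at discharge is not a good substitute. Leaving hospital unrecovered is unlikely to be independent of the time to recovery, so the censoring would be informative.

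The cost is a few sentences and one CRF tick-box. The real loss is that a mean and t-test cannot be used for these outcomes when any patient is not reached. A median remains available while fewer than half of an arm is not reached.

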8.3.2.2 Lymph node metastasis

- The number of lymph nodes in each group was used as the denominator, the number of lymph nodes in the final pathological report was used as the molecule, and the proportion of lymph node metastasis in each group was obtained. The proportion of total gastric lymph node metastasis was calculated

9 Standard operating procedures (SOP)

9.1 Case selection

9.1.1 Selection assessment items

Clinical examination data of patients conducted from hospital admission to enrollment into this study (time period is usually 2 weeks) will be considered baseline data, and must include:

- (1) Systemic status: ECOG score, height, weight, BMI, ASA score;
- (2) Peripheral venous blood: Hb、RBC、WBC、LYM、NEU、NEU%、PLT、MONO
- (3) Blood biochemistry: albumin, prealbumin, total bilirubin, indirect bilirubin, direct bilirubin, AST, ALT, creatinine, urea nitrogen, Total cholesterol, triglycerides, fasting glucose, potassium, sodium, chlorine, calcium
- (4) Serum tumor markers: CEA、CA19-9、CA72-4、CA12-5、AFP
- (5) Full abdominal (slice thickness of 10mm or less, in case of allergy to the contrast agent, CT horizontal scanning is allowed only)
- (6) Upper gastrointestinal endoscopic ultrasonography (EUS) and biopsy, if no EUS, select ordinary upper gastrointestinal endoscopy and biopsy instead
- (7) Chest X-ray (AP and lateral views): cardiopulmonary conditions(Chest CT replacement is permitted)
- (8) Resting 12-lead ECG

(9) Respiratory function tests: FEV1, FVC

9.1.2 Selection application

For cases that meet all inclusion criteria and none of the exclusion criteria, talk to patients and their families and sign informed consent. Application and confirmation of eligibility should be completed preoperatively; postoperative applications will not be accepted.

9.2 Preoperative management

- In case of any deterioration of the clinical conditions from the selection time to the expected day of surgery, whether to undergo an elective surgery as planned should be decided in accordance with the judgment of the doctor in charge; if an emergency surgery is required, the case should be withdrawn from PP set according to Withdrawal Criteria;
- For patients with nutritional risks, preoperative enteral/parenteral nutritional support is allowed.
- For elderly, smokers, high-risk patients with diabetes, obesity, and chronic cardiovascular/cerebrovascular or thromboembolic history, among others, perioperative low-molecular-weight heparin prophylaxis, lower-limb antithrombotic massage, active lower limb massage, training in respiratory function, and other preventive measures are recommended. For other potentially high-risk complications not specified in this study protocol, the doctor in charge can decide on the most appropriate approach according to clinical practice and should record it in the CRF.
- For the operative approach of the surgeries in this study should be selected by the doctor in charge according to his/her experience and the specific intraoperative circumstances.
- Preoperative fasting and water deprivation and other before-anesthesia requirements on patients should follow the conventional anesthesia program, which is not specified in this study.
- For prophylactic antibiotics, the first intravenous infusion should begin 30 minutes before surgery. It is recommended to select a second-generation cephalosporin (there are no provisions on specific brands in this study); the preparation, concentration, and infusion rate should comply with routine practice; and prophylaxis should not exceed postoperative 24 hours (special case can be extended to 48 hours) at a frequency of one infusion every 12 hours. If a patient is allergic to

cephalosporins (including the history of allergy or allergy after cephalosporin administration), other types of antibiotics are allowed according to the specific clinical situation and when used over the same period mentioned.

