
to conduct clinical research on robotic-assisted radical gastrectomy with D2 lymphadenectomy for locally advanced gastric cancer. At present, there is no prospective study report on the treatment of locally advanced gastric cancer with robot and laparoscopic D2 lymph node dissection.

Our center reported the first robotic-assisted gastrectomy in China in 2010, and has completed more than 600 cases of robotic-assisted gastrectomy. At present, there is a lack of prospective research literature reports on robot and laparoscopic radical total gastrectomy combined with D2 lymphadenectomy in the treatment of locally advanced gastric cancer, and the safety and effectiveness of robotic and laparoscopic radical total gastrectomy with D2 lymphadenectomy for locally advanced gastric cancer are still unclear. This study intends to conduct the first international prospective study of robot and laparoscopic radical total gastrectomy with D2 lymphadenectomy for the treatment of locally advanced gastric cancer, and to provide evidence-based medicine for the widespread development of robot-assisted total gastrectomy for locally advanced gastric cancer.

2. Objective

The purpose of the prospective trial is to investigate the safety and feasibility between Robotic and laparoscopic radical total gastrectomy with D2 lymphadenectomy for locally advanced gastric cancer.

3. Research design

prospective, single-center, non-randomized, controlled, non-blind, and non-inferiority observation trial

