3.2 Case group

Group A (Experimental): Robotic-assisted Total Gastrectomy with D2 Lymphadenectomy

Group B (Compared): Laparoscopic-assisted Total Gastrectomy with D2 Lymphadenectomy

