4.3 Withdraw criteria

- (16) Patients intraoperatively/postoperatively confirmed as T4b
- (17) M1 tumor confirmed intraoperatively or postoperatively: distant metastasis only found by intraoperative exploration or postoperative pathological biopsy or a positive postoperative peritoneal lavage cytology examination
- (18) Requirement of simultaneous surgery for other diseases
- (19) Patients intraoperatively confirmed as unable to complete D2 lymph node dissection/R0 resection due to tumor: unable to complete R0 resection due to regional lymph node integration into a mass or surrounded with important blood vessels, which cannot be resected
- (20) Sudden severe complications during the perioperative period (intolerable surgery or anesthesia), which renders it unsuitable or unfeasible to implement the study treatment protocol as scheduled
- (21) Patients who voluntarily quit or discontinue treatment for personal reasons at any stage after inclusion in this study
- (22) Treatment implemented is proven to violate study protocol.

5. Outcome Measures

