9.3.1.12 Regulations on conversion to laparotomy

When intra-abdominal hemorrhage, organ damage and other serious/life-threatening complications which are difficult to control occur during robotic surgery, it is necessary to actively convert to laparotomy. If the anesthesiologist and surgeon consider that intraoperative complications caused by carbon dioxide pneumoperitoneum may threaten the patient's life, it is necessary to actively convert to open. The surgeon in charge can decide to convert to laparotomy driven by other technical or equipment reasons and will record said reasons. The reasons for the conversion to open must be clearly recorded in the CRF. The incision length of > 10 cm is defined as a case of

conversion to open surgery in this study.

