11.1 Case Report Form (CRF)

11.1.1 CRF Types and Submission Deadline

CRFs used in this study and their submission deadlines are as follows:

- (1) Case Screening: 1-7 days prior to surgery (time frame of three days)
- (2) Enrolling: submitted to the data center at one day prior to surgery
- (3) Surgery: within 1 day after surgery
- (4) Postoperative discharge: within three days after the first discharge
- (5) Follow-up records: 7 days after each specified follow-up time point

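### The protocol does not fix the study group before surgery or say where a robotic operation finished laparoscopically is counted, and 9.2 can be read as letting intraoperative findings decide

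*Protocol*

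**What the plan says.** The design is "prospective, single-center, non-randomized, controlled, non-blind, and non-inferiority observation trial" (protocol section 3). The arms are identified by the operation alone: "Group A (Experimental): Robotic-assisted Total Gastrectomy with D2 Lymphadenectomy" in 3.2, and the laparoscopic counterpart for Group B.

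On timing, 9.1.2 states "Application and confirmation of eligibility should be completed preoperatively; postoperative applications will not be accepted", and 11.1.1 lists "Enrolling: submitted to the data center at one day prior to surgery". Neither mentions the group. The allocation number in 13.3 is described as a subject identifier, not as a group assignment.

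On choice of operation, 9.2 says that the operative approach "should be selected by the doctor in charge according to his/her experience and the specific intraoperative circumstances".

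On departures, 9.3.1.12 deals with conversion to laparotomy and requires that "The reasons for the conversion to open must be clearly recorded in the CRF". Item (5) of 9.3.2 is likewise limited to conversion to open surgery. Item (3) records the type of operation on the day it is done. Section 4.3 item (22) withdraws a patient when "Treatment implemented is proven to violate study protocol". Section 10.1 places all analyses on a per-protocol basis.

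**The concern.** In this trial the choice between robotic and laparoscopic surgery is the exposure being compared. Read literally, 9.2 allows that choice to be made once the operation is under way, at least a day after the enrolment form has gone in. Group membership could then depend on bleeding, poor exposure or other difficulty that also predicts the primary outcome, overall postoperative morbidity.

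This differs from ordinary baseline confounding in a non-randomized study. Adjusting for preoperative covariates cannot remove a dependence on events that happen after the first incision. Moving difficult robotic cases out of Group A lowers its complication rate, and counting them in Group B may raise the comparator's. Both push the comparison towards non-inferiority, and both hide robotic failures in a study whose stated purpose includes feasibility.

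**Working it through.** **1. What the text settles.**

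| Question | Where | Answer in the visible text |
|---|---|---|
| When is the enrolment form due? | 11.1.1 | "submitted to the data center at one day prior to surgery" |
| When is the approach chosen? | 9.2 | May depend on findings during the operation |
| What defines the group? | 3.2 | Name of the procedure; intended or received not stated |
| Robotic to laparoscopic switch? | 9.3.1.12, 9.3.2 (5) | Not mentioned; only conversion to open |
| Analysis set? | 10.1 | Per-protocol only |

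Three treatments of a switched case are compatible with this: keep it in A, count it in B, or drop it. Keeping it in A creates no bias.

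**2. The plan's own figures.** Section 3.3 gives 15% in both groups, a margin of 15 points, α = 0.05, 80% power, 68 per group, then 75. Exact binomial enumeration of the unpooled Z test at one-sided 0.05 gives power 80.03% at n = 68 (78.6% at 67), so 68 reproduces; 68 × 1.1 = 74.8, so 75. The point does not depend on these figures, and the fix leaves them unchanged.

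**3. Size of the bias, by assumption.** From the plan: N = 75 per arm and r = 15%, so 75 × 0.15 = 11.25 expected events per arm. Assumed, because the documents give neither: m switched patients with morbidity q.

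- Moved to B: A = (11.25 − mq)/(75 − m); B = (11.25 + mq)/(75 + m).
- Dropped: A as above; B = 15%.

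| m | q | A | B if moved | False advantage, moved | False advantage, dropped |
|---|---|---|---|---|---|
| 3 | 15% | 10.80/72 = 15.0% | 11.70/78 = 15.0% | 0 | 0 |
| 2 | 30% | 10.65/73 = 14.6% | 11.85/77 = 15.4% | 0.8 points | 0.4 points |
| 3 | 50% | 9.75/72 = 13.5% | 12.75/78 = 16.3% | 2.8 points | 1.5 points |
| 5 | 60% | 8.25/70 = 11.8% | 14.25/80 = 17.8% | 6.0 points | 3.2 points |

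The first row shows the condition: A falls below r only if q exceeds r. The 6.0 points are 6.0/15 = 40% of the margin.

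**4. Effect on a false conclusion, also by assumption.** Put the true rates at the margin (robotic 30%, laparoscopic 15%) and test at one-sided 0.05. With d the difference after movement to B, and SE its unpooled standard error, P(non-inferior) = Φ((0.15 − d)/SE − 1.645).

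- No switches: d = 0.150, P = 5%.
- 3 at 40%: 21.3/72 − 12.45/78 = 0.136, P = 7.5%.
- 5 at 60%: 19.5/70 − 14.25/80 = 0.100, SE = 0.0686, P = 17.8%.
- 8 at 60%: 17.7/67 − 16.05/83 = 0.071, P = 31%.

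**The case against.** The strongest reply is that the sentence in 9.2 is one more clause leaving technique to the surgeon. Section 9.3.1.7 uses very similar language for reconstruction, which is a choice within either arm, and 9.3.1.8 and 9.3.1.9 do the same for instruments and drains. Other sections (4.3 item (20), 9.3.1.11, 9.3.1.12) treat the study operation as already settled when surgery starts. This reading is tenable. It does not dispose of the point, because no other section in the visible text then says how or when the group is set.

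A reader might infer that switched robotic cases will be counted as laparoscopic. The protocol does not say so. It describes no such switch, and the case could equally stay in Group A. A reader might also infer that such a switch would leave no trace. Item (3) of 9.3.2 does record the type of operation. What is not listed is the intended operation, or a switch with its reason. Whether item (22) would remove such a case is also unclear, since a choice that 9.2 permits is hard to call a violation.

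The enrolment form itself is not shown and may already carry the planned group. The SAP, also not at hand, may define analysis by intended group, but it cannot supply an intention that nobody recorded before surgery. Finally, switches may be rare, and those made for equipment reasons need not be high risk.

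**Conclusion.** The point holds as a gap in the definition of the exposure, and it should be closed because it bears on the primary comparison. It does not show that group membership is in fact set after the operation begins, or that any patient will be reclassified.

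The direction is towards non-inferiority only under two conditions: switched cases leave Group A, and their risk is above that arm's average. Under the assumed inputs the false robotic advantage is about 0.8 to 6.0 points for 2 to 5 moved cases at 30% to 60% morbidity, and 1.5 points for 3 dropped cases at 50%. These figures illustrate sensitivity when about 11 events per arm are expected. They are not estimates for this trial, because the documents give neither a switch rate nor a risk for switched patients.

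**What to change.** - Record the intended group (A or B) on the enrolment form sent in before surgery, and analyse the primary outcome by that group.
- In 9.3.2 item (5), add robotic-to-laparoscopic conversion, with its reason, beside conversion to open.
- State that such a switch is not by itself a withdrawal under 4.3 item (22).
- Reword 9.2 so that intraoperative circumstances may change the technique used but not the study group.

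The cost is two form fields and some protocol wording. Surgical discretion and the planned 68 and 75 per group are unchanged. The downside for the sponsor is that the robotic complication rate may look less favourable, because difficult robotic starts remain in Group A.
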